Clinical Study Protocol

Protocol Number: HBCOVID-01

“A Phase II, Open Label, Single-Center, Clinical Trial to Assess Safety and Efficacy of HB-adMSCs to Provide Immune Support Against Coronavirus Disease”

IND Number:	19680
NCT Number	NCT04349631
Name of Product	HB-adMSCs Hope Biosciences Adipose Derived Mesenchymal Stem Cells
Phase of development	II
Indication	Coronavirus Disease (COVID-19)
Sponsor Contact	[name] Director of Research Hope Biosciences Stem Cell Foundation [name] [contact] [contact] [contact]
Protocol Version	1.2
Protocol Version Date	20-APR-2020

-CONFIDENTIAL-

This document and its contents are the property of and confidential to Hope Biosciences.
Any unauthorized copying or use of this document is prohibited.

Ethics and Regulatory Compliance Statement

The procedures set forth in this protocol are designed to ensure that the Hope Biosciences StemCell Foundation and principal investigator(s) abide by the International Conference on Harmonization (ICH) current Good Clinical Practice (cGCP) guidelines, current Good Laboratory Practice (cGLP) guidelines, the Declaration of Helsinki, and applicable local regulatory requirements and laws in the conduct, evaluation, and documentation of this study.

Synopsis

Title of the Study:	“A Phase II, Open Label, Single-Center, Clinical Trial to Assess Safety and Efficacy of HB-adMSCs to Provide Immune Support Against Coronavirus Disease”
Protocol Number:	HBCOVID-01
Investigators	Principal Investigator: [name] Sub-Investigator: [name]
Study Site: Single site:	Hope Biosciences [name]
Phase of development	II
Objectives	
Primary:
 
 - To investigate the efficacy of HB-adMSCs in providing immune support against development of COVID-19 by decreasing the percentage of subjects that develop symptoms of COVID-19 infection. 
Secondary:
 
 - To investigate the efficacy of HB-adMSCs in the prevention of upper and lower respiratory infections requiring hospitalization.

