Study Design:	
This phase II, open label, single-center, safety and efficacy study is designed to evaluate HB-adMSCs to support immunity against Coronavirus Disease.
 
The screening period, up to 14 days long for each patient, will be used to assess eligibility. Once eligibility is confirmed, the patient will be considered enrolled.
 
Upon study completion, the investigators should know whether or not HB-adMSCs are effective to use in this population and if it does protect against the Coronavirus Disease.
 
To ensure that the drug is safe, a Medical Monitor will oversee the entire study, review any clinically significant laboratory data, including complete blood counts, serum chemistry, adverse events.

Planned Sample Size:	
Population: 55 patients.
 
The sample size required assumes a 15% drop-out of patients.

Investigational Therapy:	HB-adMSCs (Hope Biosciences adipose-derived mesenchymal stem cells) is provided as a white-yellowish solution in a 30 ml syringe. Each 20-mL contains 2×10^8 of HB-adMSCs to be diluted in a volume of 250 mL saline solution. HB-adMSCs is to be administered by IV infusion at a rate of 83 gtt/min at Weeks 0, 2, 6, 10 and 14. Each patient shall receive 5 HB-adMSCs infusions.
Treatment Duration:	The approximate maximum duration of treatment for each patient is 14 weeks (Week 0 through 14), and the approximate duration of the study is 26 weeks.
Criteria for Evaluation:	
Safety: Safety will be assessed by adverse event (AE) reporting, physical examinations, vital signs, and clinical laboratory values. Patient safety data will be closely monitored by the clinical team to ensure patient safety, as well as the Medical Monitor and DSMB.
 
Clinical Efficacy: Efficacy will be evaluated through the analysis of Complete Blood Count with differential. Exploratory measures will include changes from baseline inflammation, SF-36 and PHQ-9.

Statistical Methods and Planned Analyses:	The statistical analysis plan is defined and enumerated.

Introduction

Study Objectives and Endpoints

Study Objectives

Primary:

- To investigate the efficacy of HB-adMSCs in providing immune support against development of Coronavirus Disease by incidence of hospitalization for COVID-19, incidence of symptoms associated with COVID-19 (ie., fever, shortness of breath/difficulty breathing, and/or cough), and severity of COVID-19 associated symptoms ((fever 38C or higher, cough, shortness of breath/difficulty breathing).

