- Patient withdrawal of consent: At any time, a patient's participation in the study may terminate at his/her request. The specific reason for patient withdrawal will be noted on the case report form (CRF).
- Lost to follow-up: The patient stops coming for visits, and study personnel is unable to contact the patient after repeated attempts (e.g., mail, or email).
- This study may be terminated at the discretion of the Sponsor or any regulatory agency.

If a patient's infusions are discontinued at any point during the trial and the patient maintains consent to contribute additional outcome information, the patient should continue to be followed through Week 26 for all safety and efficacy assessments. Investigators will be trained about the importance of retention and steps to prevent missing data.

The date and reason for withdrawal are to be documented in the CRF. The study site must immediately notify the medical monitor. The patients who withdraw prematurely must attend an early discontinuation visit if possible, at which time they will complete all assessments described in Table 2 under the Week 26 visit.

In the event that a patient discontinues prematurely from the study due to an Adverse Event (AE) or serious AE, the event will be followed until it resolves (returns to normal or baseline values) or stabilizes, or until it is judged by the Investigator to be no longer clinically significant. Once a patient is withdrawn from the study, the patient may not re-enter the study.

If the subject develops symptoms associated with COVID-19 during the conduct of this study, they will be asked to consult their personal physician and be tested for COVID-19, and to selfquarantine for at least 14 days. Quarantine must occur while waiting for COVID-19 test results. Once asymptomatic, subject may resume site visits. If the test results are positive, the subject will be asked to quarantine and may continue to receive infusions at the quarantine site. If the subject develops severe symptoms (ie., shortness of breath/difficulty breathing) they should go to the ER instead of personal physician.

Treatments

Details of the investigational product

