1. INTRODUCTION

The purpose of this Statistical Analysis Plan (SAP) is to describe the analyses to be included in the Clinical Study Report for Protocol HBCOVID-01. Details of the planned final analysis provided.

Additional detail with regards to data handling conversions and the specification of the data displays will be provided in the Programming Specifications (PS) document.

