2. SUMMARY OF KEY PROTOCOL INFORMATION

2.1. Study Objective(s), Estimand(s) and Endpoint(s)

Objectives	Endpoints
Primary Objective	Primary Endpoint

 To investigate the efficacy of HB-adMSCs in providing immune support against development of Coronavirus Disease by incidence of hospitalization for COVID-19, incidence of symptoms associated with COVID-19 (ie., fever, shortness of breath/difficulty breathing, and/or cough), and severity of COVID-19 associated symptoms ((fever 38C or higher, cough, shortness of breath/difficulty breathing). 	
 Incidence of hospitalization for COVID-19. Incidence of symptoms associated with COVID-19
Secondary Objective	Secondary Endpoint

 To investigate the efficacy of HB-adMSCs in the prevention of upper and lower respiratory infections in a high-risk population. 	
 Absence of upper/lower respiratory infections (with hospitalization criteria) up to 3 months post infusions. Change from baseline in leukocyte differential Change from baseline in C-Reactive Protein Change from baseline in TNF-alpha Change from baseline in IL-6 Change from baseline in IL-10

CONFIDENTIAL**Hope Biosciences****HBCOV01**

Objectives	Endpoints
	
• Clinically significant changes in laboratory values, vital signs, weight, and physical examination results.• Incidence of Adverse Events (AEs) and serious AEs (SAEs) related to the drug

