2.2. Study Design

Overview of Study Design and Key Features	
This phase II, open label, single-center, safety and efficacy study is designed to evaluate HB-adMSCs to support immunity against Coronavirus Disease.	
Design Features	
The trial includes,
 
 • There is a screening period of up to 14 days • A 14-week treatment period while on HB-adMSCs 
 ▪ Infusion 1 (Week 0), Infusion 2 (Week 2), Infusion 3 (Week 6), Infusion 4 (Week 10) and Infusion 5 (Week 14) • A safety Follow-up periods and end of the study or early discontinuation visit. 
 ▪ Follow up week of 18 and 22 and end of study at Week 26 • 55 Subjects
Study Intervention	
 • Intervention: HB-adMSCs (Hope Biosciences adipose derived mesenchymal stem cells) 
 ▪ Dose: 2×10^8 cells suspended in 20 ml sterile saline ▪ Route: Intravenous ▪ Regimen: Weeks 0, 2, 6, 10 and 14. ▪ 83 gts/min (250 mL/hr) • Study treatment details, 
 ▪ Each syringe contains 20 ml of cells solution with 2×10^8 cells (+20%). The syringe content is to be diluted in 250 mL of 0.9% sodium chloride.
Study Intervention Assignment	
 • All participants receive HB-adMSCs
Interim Analysis	
 • No interim analysis will be performed in this study

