3. STATISTICAL HYPOTHESES

No formal statistical hypothesis testing performed.

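### The protocol promises an answer on whether HB-adMSCs protect against COVID-19, but a single treated arm with no planned comparison can only describe incidence in treated subjects

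*Protocol*

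**What the plan says.** The Study Design row of the protocol synopsis states: "Upon study completion, the investigators should know whether or not HB-adMSCs are effective to use in this population and if it does protect" against the disease. The synopsis primary objective is to investigate efficacy "by decreasing the percentage of subjects that develop symptoms of COVID-19 infection", without saying decreased relative to what. The fuller objective, in the protocol's Study Objectives and in SAP 2.1 and 5.2.1, reads "To investigate the efficacy of HB-adMSCs in providing immune support against development of Coronavirus Disease by incidence of hospitalization for COVID-19" and goes on to the incidence and severity of symptoms.

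On design and analysis:
- SAP 2.2: "All participants receive HB-adMSCs". The protocol's infusion schedule section likewise gives the product to every eligible, enrolled patient.
- SAP 3: "No formal statistical hypothesis testing performed".
- SAP 5.2.2 summarises the two primary incidences as counts and percentages. SAP 5.1.1 plans only number and percentage for categorical variables.
- SAP 5.2 assigns the primary analysis to the efficacy set, which SAP 4 limits to subjects with all five infusions. For a subject who stops infusions but keeps consent, the protocol's withdrawal section says "the patient should continue to be followed through Week 26 for all safety and efficacy assessments".
- SAP 6 gives 55 patients and no basis. The synopsis adds a 15% drop-out assumption. On methods, the synopsis says only "The statistical analysis plan is defined and enumerated".

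**The concern.** Protection is a contrast: fewer cases with the product than there would have been without it. The protocol promises knowledge of that contrast, and the plan supplies nothing to form it. If the wording stays, a low count at Week 26 can be presented as the answer the protocol promised, although the same count could arise with an inert product in a period or population with low exposure.

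A second, smaller matter is precision. The number analysed is small, no interval is planned in the SAP text, and the primary set is defined by completing treatment. A subject who has the primary event could miss an infusion because of it and so leave the set in which events are counted.

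**Working it through.** **1. Is there a comparator?** Each place that could supply one:

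| Possible source | What the documents give |
|---|---|
| Concurrent control | None; all are treated (SAP 2.2) |
| Hypothesis or threshold | None; no formal test (SAP 3) |
| Reference rate in the analysis | None; counts and percentages (SAP 5.2.2) |
| Reference rate in the sample size | None; 55 only (SAP 6) |
| Comparison named in SAP 5.2 | Placebo on MDS-UPDRS Part II; neither that arm nor that endpoint exists in this trial |
| Change-from-baseline markers (SAP 5.3.1) | Within-subject description; secondary, and not an infection outcome |

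**2. The plan's own figure.** The 55 cannot be reproduced, because no expected incidence, precision target, error rate or power is given. Only the drop-out step can be checked: 46 / (1 − 0.15) = 54.1, rounded up to 55. In the other direction, 55 × 0.85 = 46.75, taken below as 47. Using 47 for the efficacy set is an assumption, because dropping out is not the same as missing an infusion.

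**3. Precision by number analysed.** Intervals are exact (Clopper-Pearson), two-sided 95%. For zero events the upper limit is 1 − 0.025^(1/n); for n = 55 this is 1 − 0.025^(1/55) = 6.49%. The widest interval is the maximum over all possible counts.

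| Analysed | Upper limit at 0 events | Widest interval |
|---|---|---|
| 55 | 6.5% | 27.6 points |
| 47 (illustrative) | 7.5% | 29.9 points |
| 40 (illustrative) | 8.8% | 32.4 points |

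**4. What a count would mean at an assumed reference rate.** The documents give no rate, so a range is shown. The entry is the largest number of events whose upper limit falls below the rate.

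| Assumed rate | Of 55 | Of 47 |
|---|---|---|
| 5% | none (0 events gives 6.5%) | none (0 events gives 7.5%) |
| 10% | 1 (upper 9.7%; 2 gives 12.5%) | 0 (upper 7.5%; 1 gives 11.3%) |
| 20% | 5 (upper 19.95%; 6 gives 22.2%) | 3 (upper 17.5%; 4 gives 20.4%) |
| 30% | 9 (upper 28.8%; 10 gives 30.9%) | 7 (upper 28.3%; 8 gives 30.8%) |

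**5. The best possible result under an inert product.** The chance of zero events in 55 is (1 − p)^55. For assumed untreated incidences p of 1%, 2%, 5% and 10% it is 0.58, 0.33, 0.06 and 0.003. The same result is unremarkable or striking depending on a rate that the plan does not state.

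**6. Can the event affect membership of the efficacy set?** The pre-infusion telephone check asks a symptomatic subject to stay home. The withdrawal section asks for at least 14 days of self-quarantine, and visit windows are ±3 days. An infusion could therefore be missed because of the primary event. The protocol also allows infusions at the quarantine site after a positive test, so loss from the set is possible but not automatic.

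**The case against.** The strongest defence is that this is a declared descriptive, early-phase study: the SAP says outright that nothing is tested, and no decision rule depends on the synopsis sentence. That stands as a defence of the design. It does not defend the sentence or the objectives, which claim more than a descriptive design can deliver.

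A reader might infer that no reference rate exists at all. The documents do not support that. The text of the protocol's Introduction is not in the supplied copy and could contain a background rate. What can be said is that the supplied SAP analysis sections compare the incidences with none.

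A reader might also infer that uncertainty will be hidden. That goes too far. Anyone can compute an exact interval from a count and its denominator, and SAP 1 says "the specification of the data displays will be provided in the Programming Specifications (PS) document", so an interval may be planned there. Stating it in the SAP is good practice rather than the repair of a fatal gap.

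The synopsis also says that efficacy will be evaluated through the blood count with differential, and marker changes from baseline can be described. Neither shows that COVID-19 was prevented.

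Finally, the placebo sentence in SAP 5.2 matches neither this design nor its endpoints. It is a separate error to correct, not evidence of a hidden comparison.

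**Conclusion.** The mismatch between claim and design holds. The primary endpoints can describe the incidence of COVID-19 symptoms and hospitalization in treated subjects, and in the planned primary analysis only in those with all five infusions. They cannot establish protection.

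The size of the problem depends on the number analysed. The limits of 6.5% at zero events and 27.6 points at the widest apply only if all 55 are analysed; the planned primary set is likely to be smaller. The reference rates and the sizes 47 and 40 are assumptions for illustration. The conclusion about protection does not rest on them, only on the absence of any planned comparison.

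This does not make a single-arm study illegitimate, and it does not show that the efficacy set will in fact lose events. The correction should be made, and it is mainly one of wording and reporting.

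**What to change.** 1. **Wording.** Replace the synopsis sentence with: *The study will estimate the incidence of COVID-19 symptoms and hospitalization in treated subjects; without a control or a justified reference rate it does not determine whether HB-adMSCs protect.* Recast the primary objective (synopsis, Study Objectives, SAP 2.1 and 5.2.1) and the secondary objective on respiratory infections (synopsis, Study Objectives, SAP 2.1) as estimation. Symptom severity is in the fuller primary objective but has no listed endpoint: either describe it as an outcome or drop it from that objective. Replace the placebo/MDS-UPDRS sentence in SAP 5.2 with the aligned objective.
2. **SAP 5.2.2.** Report both primary incidences with exact 95% intervals, in all treated subjects (safety set) as well as in the five-infusion set, and show the number followed to Week 26. The current text places the count after Week 26; state the window as from first infusion through Week 26.
3. **SAP 6.** State precision by number analysed, using the 55, 47 and 40 rows in the working and labelling the last two as illustrative.

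The alternative is to pre-specify a justified reference rate and success threshold before outcomes are reviewed. That would support only a benchmark comparison, and blindness to outcomes is hard to assure in an open-label, single-site study.

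Cost: a protocol amendment for the objectives, SAP edits, a few extra table rows and a more modest stated aim. No extra subjects, visits or tests.

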Secondary:

- To investigate the efficacy of HB-adMSCs in the prevention of upper and lower respiratory infections in a high-risk population.

Study Endpoints

Primary endpoints:

- Incidence of hospitalization for COVID-19.
- Incidence of symptoms associated with COVID-19

Secondary endpoints:

- Absence of upper/lower respiratory infections (with hospitalization criteria) up to 3 months post infusions.
- Change from baseline in leukocyte differential
- Change from baseline in C-Reactive Protein
- Change from baseline in TNF-alpha
- Change from baseline in IL-6
- Change from baseline in IL-10
- Clinically significant changes in laboratory values, vital signs, weight, and physical examination results.
- Incidence of AEs (AEs) and serious AEs (SAEs) related to the drug

Investigational Plan

This Phase II, open label, single center, assesses efficacy in a population of patients who have already banked their cells to evaluate HB-adMSCs to provide immune support against Coronavirus Disease. It is designed to be conducted over 3 periods or phases:

- **Phase 1** (Screening): Our screening process starts with a telephone call to provide a general overview of the study and discuss eligibility requirements. The study patient will receive the informed consent document by e-mail or in the pre-paid envelope provided. If, after reviewing this consent the study patient is still interested in participating in the study, he/she will need to sign and return the consent form to Hope Biosciences Stem Cell Research Foundation. This process can take up to 14 days.
- **Phase 2** (Treatments): Includes Infusion 1 (Week 0), Infusion 2 (Week 2), Infusion 3 (Week 6), Infusion 4 (Week 10) and Infusion 5 (Week 14). Subjects will be monitored at the clinical site for 1 hour following HB-adMSCs administration.
- **Phase 3** (follow-up): Includes Follow Up Week 18, 22 and End of Study at Week 26.

Safety assessments will be ongoing. A follow up phone call will be done a day after every infusion. Blood tests will include Complete Blood Count with differential, Comprehensive Metabolic Profile and Coagulation Panel screening for hepatotoxicity, cytopenia, renal failure or alterations in the coagulation cascade that might entail a safety concern for the individual. Efficacy assessments will include PHQ-9, SF-36, TNF-a, IL-6, IL-10, and CRP.

Selection and Withdrawal of Patients

Inclusion Criteria

1. Men and women 65 years of age and older (according to CDC provisions) OR

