The investigators should document all prior significant medical history. Additional conditions present at the time when informed consent is given and up to the time of first infusion (Week 0) are to be regarded as concomitant conditions.

Illnesses first occurring or detected during the study and/or worsening of a concomitant condition during the study should be documented as AEs in the CRF.

Prior and concomitant medications

All medications, including over-the-counter treatments and preventative vaccines taken by the patient during the study, including those treatments initiated prior to the start of the study, must be recorded in the CRF. The entry must include the dose, regimen, route, indication, and dates of use.

Study Procedures

Table 2 outlines the timing of procedures, and assessments to be performed throughout the study.

Table 2. Schedule of Assessments

Visit Number	1	2	3	4	5	6	7	8	9
Weeks	N/A	Week 0	Week 2	Week 6	Week 10	Week 14	Week 18	Week 22	Week 26
Visit Name	Screening (Phone call)	Infusion- 1 /Baseline	Infusion 2	Infusion 3	Infusion 4	Infusion 5	Follow Up	Follow Up	EOS
Window Period	Up to 14 days	± 3 days	± 3 days	± 3 days	± 3 days	± 3 days	± 3 days	± 3 days	± 3 days

STUDY PROCEDURES

Informed Consent	X	X							
Inclusion and Exclusion Criteria	X	X							
Pre-infusion assessment		X	X	X	X	X			
Review of Medical History	X	X	X	X	X	X	X	X	X
Concomitant Medication Review	X	X	X	X	X	X	X	X	X
Vital Signs		X	X	X	X	X	X	X	X
Weight and Height ¹		X	X	X	X	X	X	X	X
Physical Examination		X	X	X	X	X	X	X	X
SF-36 Questionnaire		X	X	X	X	X	X	X	X
PHQ-9		X	X	X	X	X	X	X	X
Rapid antibody COVID-19		X							X
CBC with differential		X		X		X			X
Chemistry		X		X		X			X
Coagulation Panel		X		X		X			X
CRP		X		X		X			X
IL-6		X		X		X			X
IL-10		X		X		X			X
TNF α		X		X		X			X
HB-adMSCs Administration		X	X	X	X	X			
24-hour telephone encounter		X	X	X	X	X			
Adverse Event Monitoring		X	X	X	X	X	X	X	X

¹ Height will only be measured at baseline

Informed Consent (ICF)

Prior to commencement of any trial related activity, the investigator or designated staff will obtain written informed consent from the patient.

Patient Re-Screening

If a patient is screened and fails to meet any study entry criteria may be re-screened only once. Such patient must be fully consented a second time before the second set of screening assessments take place and shall be assigned a new subject number. Investigator discretion should be exercised in determining who may be re-screened.

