If a patient is enrolled after they have been re-screened, such subject shall be assigned a new subject ID number, different from the previous attempt to enroll.

Assessments by Week

Assessments will occur as outlined in the following subsections. For visits at Weeks 0 through 26, there will be a window of ± 3 days.

Screening

The Screening visit will last up to 14 days. These are the procedures to be performed during this visit:

- Demographic Information will be obtained.
- Medical History and Current conditions will be obtained,
- Concomitant Medications will be obtained. Every medication listed should match a condition in the medical history.
- Ascertain patient eligibility by evaluating patient results against the inclusion/exclusion criteria.

Upon completion of all Screening procedures, the Principal Investigator must confirm and document the patient eligibility in the “Screening Result” CRF and notify the Sponsor via Fax or e-mail.

Infusion Visits (Baseline/Week 0, Week 2, Week 6, Week 10, and Week 14)

Generally, these are the procedures to be performed at every infusion visit. For details please refer to the schedule of assessments.

Baseline assessments will be taken before the administration of the first infusion. A second assessment of informed consent shall be obtained prior to the first infusion.

- Pre-infusion assessment will be made by telephone call in the morning prior to all infusion visits to assess any occurrence of symptoms. In the event a subject is exhibiting symptoms, the subject will be asked to remain home.
- Weight and height will be measured
- Vital Signs will be measured.
- Concomitant medications will be reviewed and updated if necessary.
- Medical History will be reviewed and updated if necessary. If the patient reported a medication which does not match the current medical history, further investigation will be required to determine whether it was added due to an Adverse Event, or the patient just forgot to mention it before. If it is found to be an AE, it should be recorded in the appropriate CRF. If the patient forgot to mention it before, a note to file (NTF) should be made to clarify the case.
- Blood will be collected for laboratory assessments at weeks 0, 6, and 14.
- Physical examination performed by principal investigator or sub-investigator.
- Administer investigational product.

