- Monitor for AEs. Observe the patient for at least 1 hours after infusion for symptoms of infusion-related reactions and allergic reactions, including anaphylaxis (See Appendix 1).
- Instruct the patient on recognition of delayed serious allergic reactions, including anaphylaxis and seeking for medical assistance.
- Telephone encounter 24 hours after the infusion will be performed to assess the occurrence of AEs.

Follow Up Weeks 18, and 22.

- Weight will be measured
- Vital Signs will be measured.
- Concomitant medications will be reviewed and updated if necessary.
- Medical History will be reviewed and updated if necessary. If the patient reported a medication which does not match the current medical history, further investigation will be required to determine whether it was an Adverse Event, or the patient just forgot to mention it before. If it is found to be an AE, it should be recorded in the appropriate CRF. If the patient forgot to mention it before, a note to file (NTF) should be made to clarify the case.
- Physical examination performed by principal investigator or sub-investigator.

Weeks 26 (End of the Study or Early Discontinuation Visit)

- Weight will be measured
- Vital Signs will be measured.
- Concomitant medications will be reviewed and updated if necessary.

- Medical History will be reviewed and updated if necessary. If the patient reported a medication which does not match the current medical history, further investigation will be required to determine whether it was an Adverse Event, or the patient just forgot to mention it before. If it is found to be an AE, it should be recorded in the appropriate CRF. If the patient forgot to mention it before, a note to file (NTF) should be made to clarify the case.
- Blood samples will be collected.
- Physical examination performed by principal investigator or sub-investigator.

If a patient prematurely withdraws from the study for any reason, the early discontinuation visit requirements should be completed. If the early discontinuation visit is not done, the reason(s) will be recorded in the CRF.

Unscheduled Visits

The Investigator may at his/her discretion arrange for a patient to have an unscheduled assessment, especially in the case of adverse events (AEs) that require follow-up, or an AE considered by the Investigator to be possibly related to the use of the investigational product. The unscheduled visit page in the CRF must be completed.

Efficacy Assessments

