An AE is any symptom, physical sign or disease that either emerges during the study or, if present at screening, worsens during the study, regardless of the suspected cause of the event. All medical and psychiatric conditions (except those related to the indication under study) present at screening will be documented in the medical history CRF. Changes in these conditions and new symptoms, physical signs, or diseases should be noted on the AE CRF during the rest of the study.

Clinically significant laboratory abnormalities should also be recorded as AEs. Surgical procedures that were planned before the patient enrolled in the study are not considered AEs if the conditions were known before study inclusion; the medical condition should be reported in the patient's medical history.

Serious Adverse Events (SAE)

A serious adverse event (SAE) is any AE that is:

- fatal
- life-threatening
- requires or prolongs hospital stay
- results in persistent or significant disability or incapacity
- Important Medical Events (IME): those events that may not result in death, be immediately life threatening, or require hospitalization. They may be considered a SAE when, based upon medical judgement, they may jeopardize the subject and may require intervention to prevent one of the other serious outcomes noted above. For example, drug overdose or abuse, a seizure that did not result in in-patient hospitalization, or intensive treatment of bronchospasm in an emergency department would typically be considered serious. (FDA, 21CFR312.32; ICH E2A and ICH E6)

All SAEs must be reported to Hope Biosciences immediately after the Investigator becomes aware of the event, along with a determination as to whether it is associated with the study drug. Patients will be instructed to report AEs at each study visit. All AEs are to be followed until resolution or until a stable clinical endpoint is reached.

Each AE is to be documented in the CRF with reference to onset date, duration, frequency, severity, relationship to study drug, treatment of event, and outcome. Furthermore, each AE is to be classified as being serious or non-serious. Changes in AEs and resolution dates are to be documented in the CRF.

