4. An infusion related, sustained (over 3 minutes) episode of hypoxia (SaO₂ of less than 80%).
5. Any Grade 4-5 Adverse Event as defined in the NCI CTCAE v4.0 and determined to be temporally related to the HB-adMSC infusion by the Medical Safety Monitor and/or DSMB.

After such review, resumption of dosing may be considered, including consideration for any prophylactic interventions (e.g. antihistamines or corticosteroids for injection site reactions).

Regarding SARS-CoV-2 infection, participants will be monitored for vital signs and physical examination at every visit. If the PI suspects possible COVID-19, it is at the PI's discretion to order testing. In the event the participant test results are positive for COVID-19, they will be allowed to complete treatment with quarantine site infusion visits only.

Protocol Deviations

An Investigator may not knowingly deviate from the study protocol without prior approval by Hope Biosciences and/or the IRB unless the deviations are necessary under emergency circumstances to protect the rights, safety, or well-being of human subjects or the scientific integrity of the clinical investigation. Deviations must be documented and promptly reported to Hope Biosciences and, if applicable, to the IRB providing oversight of the study.

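### The symptom primary endpoint has no structured assessment through Week 26; the one explicit symptom prompt is a pre-visit call that ends at Week 14

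*Protocol*

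**What the plan says.** The protocol's primary endpoints are COVID-19 hospitalization and "Incidence of symptoms associated with COVID-19". SAP 5.2.2 summarises both as counts and percentages at the end of study, which I read as cumulative to Week 26.

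The protocol's Efficacy Assessments section covers the blood count, CRP, SF-36, PHQ-9 and three cytokines. It has no entry for symptoms.

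Explicit questioning about symptoms appears once, under Infusion Visits: "Pre-infusion assessment will be made by telephone call in the morning prior to all infusion visits to assess any occurrence of symptoms". The stated consequence follows: "In the event a subject is exhibiting symptoms, the subject will be asked to remain home". Table 2 marks this assessment at Weeks 0, 2, 6, 10 and 14 only. The other call also belongs to infusions: "Telephone encounter 24 hours after the infusion will be performed to assess the occurrence of AEs".

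Other routes continue to Week 26. Table 2 marks "Adverse Event Monitoring", medical history review, vital signs and physical examination at Weeks 18, 22 and 26. The definition is broad: "An AE is any symptom, physical sign or disease that either emerges during the study or, if present at screening, worsens during the study". Patients are told to report AEs at visits, and collection runs to Week 26. The Study Stopping Rules section adds that "participants will be monitored for vital signs and physical examination at every visit". However, the procedure list headed "Follow Up Weeks 18, and 22" and the Week 26 list do not mention AE monitoring.

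SAP 5.3.2.1 closes the treatment-emergent window on the last infusion day and presents all other AEs in listings.

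**The concern.** A primary endpoint that counts symptoms needs a stated way to collect them: which symptoms, over what interval, on which form. None is given for any period. The one prompt that names symptoms works as a gate for the visit. No text links it to the endpoint, and it stops when infusions stop. For the last 12 of 26 weeks (46%), a mild cough or fever that came and went between visits enters the data only if the patient volunteers it.

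The trial has no control arm, so missed episodes do not cancel between groups. Each one lowers the reported percentage, and a low percentage is what would be read as protection. Data not collected cannot be recovered at the analysis stage.

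**Working it through.** The documents state no figure for symptom capture, so there is none to reproduce. Two checks follow.

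**1. Scheduled contacts (Table 2 and the visit lists)**

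| | Weeks 0–14 | After Week 14 to Week 26 |
|---|---|---|
| Explicit symptom calls | 5 | 0 |
| 24-hour AE calls | 5 | 0 |
| Visits with AE monitoring marked | 5 | 3 |
| Post-baseline visits per week | 4/14 = 0.29 | 3/12 = 0.25 |

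From Week 2 onward, visits are four weeks apart in both periods. The extra calls fall on the infusion day or the day after.

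**2. Share of episodes caught if nothing already resolved is recalled**

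Assumptions: onset is uniform over time, each episode lasts D days, and an episode is caught only if a contact day falls while it is active.

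- Visit days are 0, 14, 42, 70, 98, 126, 154 and 182. Next-day calls are on days 1, 15, 43, 71 and 99.
- The treatment period runs from day 0.5 to 98.5 (98 days) and follow-up from day 98.5 to 182.5 (84 days).
- A visit alone catches onsets over D days. A visit plus next-day call catches D + 1 days.

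For D = 7:
- Treatment: 0.5 (day 1 call) + 3 × 8 (Weeks 2, 6, 10) + 7.5 (Week 14, cut at the period boundary) = 32; 32/98 = 33%.
- Follow-up: 0.5 (day 99 call) + 3 × 7 = 21.5; 21.5/84 = 26%.
- Visits only: 4 × 7/98 = 29% versus 3 × 7/84 = 25%.

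For D = 14:
- Treatment: 14.5 + 15 + 15 + 14.5 = 59; 59/98 = 60%.
- Follow-up: 0.5 + 3 × 14 = 42.5; 42.5/84 = 51%.

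For D = 28, the shares are 100% and 99%.

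With full recall since the last visit, the share is 100% in both periods for every D.

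**What this shows**

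The between-period gap for 7-day episodes is at most about 7 percentage points. Over the whole study the no-recall share is (32 + 21.5)/182 = 29%, so about 71% of 7-day episodes would be missed. In both periods the endpoint depends far more on whether patients are asked about the interval since the last visit than on the number of contacts. No section requires that question.

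**The case against.** The strongest reply is that symptom collection does not stop at Week 14. A new cough, fever or breathlessness is an AE by definition. AEs are collected at every visit to Week 26, with history review, vital signs and examination alongside. Subjects who develop COVID-19 symptoms at any time are directed to a physician and a test. The visit lists are also not exhaustive: they omit SF-36 and PHQ-9, which Table 2 marks at the same visits, and the Safety Assessments section refers to Table 2 for AEs. All of this stands. A reader might infer that symptoms go uncollected in follow-up, and the documents do not support that.

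A reader might also set 15 scheduled contacts before follow-up against 3 within it and conclude that follow-up is watched several times less closely. That count treats a morning call, the visit and a next-day call as three separate looks, although they form one cluster. Post-baseline visit frequency is nearly equal.

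Finally, the SAP plans one overall percentage, with no comparison of treatment with follow-up and no hypothesis test.

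These replies leave the main gap in place. General AE reporting relies on the patient volunteering events. Vital signs and examination mainly show what is present that day. The physician route names no form for the episode or test result. No section says which record supplies the endpoint.

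**Conclusion.** The point holds as a gap in data collection for a primary endpoint. No symptom tool, recall interval or source record is defined in any period, and the only explicit symptom prompt ends at Week 14. If AE records are the intended source, episodes starting in follow-up would appear only in listings under SAP 5.3.2.1.

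Mild episodes may be missed, and the effect of missing them is one-directional. It would be too strong to say that incidence is understated in follow-up, because that depends on recall. For 7-day episodes the capture gap ranges from 33% versus 26% with no recall to none with full recall. Episode length, recall and uniform onset are my assumptions, not the documents'. Nothing here shows an effect on the hospitalization endpoint or changes the sample size. I rate this as a cheap improvement.

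**What to change.** 1. At every existing visit from Week 0 to Week 26, complete one fixed symptom page: fever 38C or higher, cough, and shortness of breath or difficulty breathing since the last visit, with onset, end, intensity, and any COVID-19 test and its result. Week 0 serves as baseline. The early discontinuation visit already follows the Week 26 assessments, so it would include the page.
2. In SAP 5.2.2, name that page as the source of the symptom endpoint. State that all post-baseline episodes through Week 26 count, whether or not they fall in the treatment-emergent window.
3. Align the Week 18/22 and Week 26 procedure lists with Table 2 on AE monitoring.

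The page does not equalise the number of contacts, and four-week recall remains imperfect. It does put the same question about the same kind of interval in both periods, which the current plan does not.

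Cost: one case report form page and about a minute per visit, with no new visit, staff or test. More mild events will be recorded, so the reported incidence may rise.
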